14.1 Adverse Events

Adverse events (AEs) will be coded according to the Medical Dictionary for Regulatory Activities (MedDRA), Version 21.0.

Treatment emergent adverse event (TEAE) is any condition that was not present prior to treatment with the study product but appeared following first dose in Part A, was present at treatment initiation but worsened during treatment, or was present at treatment initiation but resolved and then reappeared while the individual was on treatment (regardless of the intensity of the AE when the treatment was initiated). See [Appendix 2](#) for handling of completely or partially missing dates for AEs. In the case where it is not possible to define an AE as treatment emergent or not, the AE will be classified as treatment emergent. AEs will be considered in Part A or Part B depending on the onset date – if the AE onset date was on or before week 16 the AE will be considered as a Part A AE. If the AE had an onset after week 16 the AE will be considered as a Part B AE. AEs emerged in part A and last into part B would be reported in both parts A and B and be noted in the part B report for these AEs which are reported twice.

An overall summary table of adverse events will be provided. The number of events and the number and percentage of subjects who experienced AE, TEAE, TEAE by greatest reported relationship, TEAE by relationship, TEAE by highest reported severity, TEAE by severity, related TEAE by highest reported severity, related TEAE by severity, serious AE, serious TEAE, serious TEAE by greatest relationship, TEAE and related TEAE leading to study drug discontinuation, TEAE and related TEAE leading to study discontinuation, TEAE and related TEAE leading to treatment interruption and AE leading to death will be presented as well as TEAE of clinical interest.

TEAE of clinical interest are:

- Thrombotic events

PPD	STATISTICAL ANALYSIS PLAN, Version Final 1.0
Protocol Number: ASN002AD-202 V6.0	Sponsor: Asana BioSciences, LLC

- Serious infection
- Malignancy and lymphoproliferative disorders
- Gastrointestinal perforation
- Hypersensitivity
- Anemia
- Neutropenia
- Lymphopenia
- Liver enzyme elevation
- CPK and lipid elevation

Unless otherwise specified, a subject experiencing the same TEAE multiple times will be counted only once for the corresponding PT. Similarly, if a subject experiences multiple TEAEs within the same SOC, the subject will be counted only once for that SOC. TEAEs will be sorted alphabetically by SOC and within each SOC the PT will be presented by decreasing order.

Frequency and percentage of subjects who experience TEAE will be summarized by SOC and PT within SOC.

Frequency and percentage of subjects who experience TEAE will be summarized by SOC, PT, and relationship. A treatment-related TEAE is defined as any TEAE that is assessed by the investigator as probably or possibly related to study treatment. TEAE that is assessed as not related will be defined as not treatment-related. If a subject experiences more than one TEAE within different relationship categories within the same SOC/PT, only the worst case (greatest reported relationship) will be reported. A TEAE with an unknown relationship will be considered as treatment-related.

Frequency and percentage of subjects who experience TEAE will be summarized by SOC, PT, and severity (mild/moderate/severe). If a subject experiences more than one TEAE within different severity categories within the same SOC/PT, only the worst case (highest reported severity) will be reported. TEAE with an unknown severity will be considered as severe.

Frequency and percentage of subjects with TEAEs will be summarized by SOC, PT, relationship, and severity (mild/moderate/severe). Each subject will be counted only once within a System

PPD	STATISTICAL ANALYSIS PLAN, Version Final 1.0
Protocol Number: ASN002AD-202 V6.0	Sponsor: Asana BioSciences, LLC

Organ Class or a Preferred Term by using (1) the greatest reported relationship followed by (2) the highest reported intensity. TEAE with an unknown severity will be considered as severe.

Frequency and percentage of subjects who experience serious TEAE will be summarized by SOC and PT within SOC.

Frequency and percentage of subjects who experience serious TEAE will be summarized by SOC, PT, and relationship. If a subject experiences more than one serious TEAE within different relationship categories within the same SOC/PT, only the worst case (greatest reported relationship) will be reported.

Proportion of subjects withdrawing for worsening of their CHE will be summarized at Weeks 4, 8, 12, and 16. Summary of Most Frequent TEAE, defined as the 1% most prevalent TEAEs, will also be summarized.

Listings of all AEs, all AEs leading to death, all serious AEs, all TEAEs leading to study drug discontinuation, all TEAEs leading to study drug interruption all TEAEs leading to study discontinuation and all most frequent TEAEs will be provided.

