^d Including height, weight and BMI. Height will be measured only at screening and the same value will be used for BMI calculation at other visits.

^e ECG will be recorded at 0 (pre-dose, within 1 hour prior to dosing), 1 (\pm 30 min), and 3 (\pm 1 hour) hours post-dose on Day 1, Week 4, Week 16 and Week 20. ECG will be recorded only once at screening, Weeks 8, 24 and 32 and ET visit (if applicable).

^f Only at ET

^g If PPD is used, a second screening visit will be necessary.

^h mTLSS, Extent of Disease and PGA to be assessed only for hands and feet, but evaluated separately.

ⁱ Microbiome samples will be collected for all subjects prior to tape stripping collection and skin biopsy (if applicable). Microbiome samples will be collected on Day 1, Week 4 and Week 16 (or ET visit, if applicable) (one from lesional skin (palmar aspect (when possible) of the worst hand) and one from adjacent nonlesional skin). At each visits samples should be collected from the same areas selected on Day 1. Microbiome samples should be collected prior to study product administration and after photographs, if applicable. If the subject has presence of foot eczema on Day 1, microbiome samples (lesional and non lesional) will be collected from the plantar aspect (when possible) of the worst foot.

^j Only at ET, if ET visit is performed prior to Week 16.

^k Skin tape stripping samples will be collected for all subjects as close as possible to the site of microbiome collection (preferably the same palmar lesion when possible) and of the skin biopsy (if applicable). Skin tape stripping samples will be collected on Day 1 (one from lesional skin and one from adjacent nonlesional skin) and one at Week 4 and Week 16 (or ET visit, if applicable) (from same lesional area as Day 1). Tape stripping should be collected prior to study product administration and after photographs, if applicable. If the subject has presence of foot eczema on Day 1, skin tape stripping samples will also be collected from the foot (one from lesional skin and one from adjacent nonlesional skin) at Day 1 and one at Week 4 and Week 16 (or ET visit, if applicable) from same lesional skin as Day 1.

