6 TREATMENT

6.1 Study Treatment Administered

This study involves two different doses of ASN002 (40 mg and 80 mg) both orally administered once daily compared to a placebo in Part A (first 16 weeks of treatment). Then, only active products (ASN002 40 mg and 80 mg) will be administered in Part B. ASN002 will be available in 20-mg strength tablets. All study products will be provided by the sponsor. All study products will be self-administered orally, at home or at the clinic on clinic visit days.

Study products administration will occur daily for 32 weeks at approximately every 24 hours, on an empty stomach (2 hours before and 2 hours after a meal) with approximately 240 mL of water. On visit days, the study products will be administered at the study center, except at Week 18. The date and time of the drug administration and fasting conditions will be collected by the study site on the visit days. When dosing at home, the subject will be instructed to take the study product at approximately the same time of the day and compliance will be self-reported during each study visits.

Further details regarding the study products for Part A can be found in [Table 2](#).

Table 2. Study Products

	Study Products		
Product name	ASN002	ASN002	Placebo (Part A only)
Dosage form	Tablet	Tablet	Tablet
Dosage level(s)	40 mg	80 mg	N/A
Unit dose strength(s)	20 mg	20 mg	N/A
Number of tablets per dose level	2 active and 2 placebo	4 active	4 placebo
Route of administration	Oral	Oral	Oral
Dosing instructions	Once a day with approximately 240 mL of water	Once a day with approximately 240 mL of water	Once a day with approximately 240 mL of water
Source of procurement	Asana BioSciences, LLC	Asana BioSciences, LLC	Asana BioSciences, LLC

The contents of the label will be in accordance with all applicable regulatory requirements.

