8.4.5 Electrocardiogram

Twelve-lead ECGs will be performed as a safety assessment at the visits specified in [Table 1](#). Clinically significant findings in the ECG should exclude a subject from study participation (as deemed appropriate by the investigator). Any clinically significant findings will be reported as an AE.

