ⁿOptional, only for a subset of approximately 36 subjects who consent: PD samples to be drawn as trough samples prior to study product administration. Subjects consenting to PD samples must also consent to biopsies. PD samples should be collected prior to study product administration.

^oPK samples will be collected at 0 (pre-dose), 2 (± 30 min) hours post-dose and 6 hours post-dose (between 5 to 12 hours post-dose). The dosing time for the previous day should be recorded accurately.

^pPK samples will be collected at 0 (pre-dose) and 2 (± 30 min) hours post-dose. The dosing time for the previous day should be recorded accurately. At ET visit (if applicable), only one PK sample will be collected.

PPD**STATISTICAL ANALYSIS PLAN, Version Final 1.0**

Protocol Number: ASN002AD-202 V6.0

Sponsor: Asana BioSciences, LLC

Study Visits	Screening	Treatment Period								Follow-up / EOT		
		Part A				Part B						
Day (D); Week (W)		D1 (D15)	W2 (D29)	W4 (D57)	W8 (D85)	W12 (D113)	W16 (D127)	W18 (D141)	W20 (D169)	W24 (D197)	W28 (D225)	W32 (D253)
Window (days)	-30 to -1		±1	±1	±2	±2	±2	±2	±2	±2	±2	±2

^q Study products will be taken at home daily for 32 weeks, except on study visit days when the study products will be administered on site. For visit Week 18, subjects will dose at home.

^r Emollient use must be initiated at least 1 week prior to Day 1.

^s On this visit, subject who were receiving placebo since Day 1, will start receive ASN002 80 mg until EOT visit.

^t Subject should be instructed to always bring their medication to the site when there is a scheduled visit.

^u On Week 2 visit, there will be no collection/dispensing, but subject will dose on site with the medication kit dispensed on Day 1.

^v Optional, only for a subset of approximately 36 subjects who consent. Photographs should be performed prior to drug administration, biopsy (if applicable) and tape stripping and microbiome sample collection.

PPD	STATISTICAL ANALYSIS PLAN, Version Final 1.0
Protocol Number: ASN002AD-202 V6.0	Sponsor: Asana BioSciences, LLC

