5.2 Baseline

Unless otherwise specified, baseline value will be defined as the last non-missing assessment prior to or on the first study treatment application date (including unscheduled assessments) in Part A. If the last non-missing assessment is performed on the same date as the first study treatment and time is not available, the assessment will be considered as baseline, except for adverse events (AEs) and medications starting on the first study treatment dose date which will be considered post-baseline.

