10 PRIOR AND CONCOMITANT MEDICATIONS

Medications will be coded according to the World Health Organization Drug Dictionary (WHO-DD), March 2018 B3.

Prior medications are defined as any medications started and discontinued prior to the first study treatment dose. Concomitant medications are defined as any medications taken from the first study treatment dose throughout the end of the study including those started prior to the first study treatment date and continued past that date. See Appendix 2 for handling of completely or partially missing dates for prior and concomitant medications.

Incidence of prior medications will be tabulated by Anatomical Therapeutic Chemical Classification System (ATC) level 3, and PT using the safety population. Incidence of concomitant medications will be tabulated in the same way but presented separately for Part A and Part B using

PPD	STATISTICAL ANALYSIS PLAN, Version Final 1.0
Protocol Number: ASN002AD-202 V6.0	Sponsor: Asana BioSciences, LLC

the safety population. Concomitant medications for Part A are defined as any medications taken after the first dose of treatment and on or before or at week 16 visit, including those that started prior to the first dose of treatment date and continued past that date. Concomitant medications for Part B are defined as any medications taken after week 16, including those started prior to week 16 and continued past that date. A subject with the same medication taken multiple times will be counted only once for the corresponding PT. Similarly, if a subject has taken more than one medication within the same ATC level, then the subject will be counted only once for that ATC.

A listing of all prior and concomitant medications will be provided.

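### SAP 14.1 counts an adverse event that starts after a placebo subject's first ASN002 dose on the Week 16 visit day under Placebo (minor; descriptive safety tables only)

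*SAP*

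**What the plan says.** **Allocation rule.** SAP 14.1 uses the onset date: "if the AE onset date was on or before week 16 the AE will be considered as a Part A AE". Later onsets belong to Part B. An AE that emerges in Part A and continues into Part B is reported in both, with a note in the Part B report. SAP 14 presents AEs separately by part, under the treatment first assigned. SAP Appendix 1 names the relevant Part A column Placebo.

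**Timing of the switch.** SAP 3.2, footnote s, says of the Week 16 visit: "On this visit, subject who were receiving placebo since Day 1, will start receive ASN002 80 mg until EOT visit". Protocol 6.1 adds: "On visit days, the study products will be administered at the study center, except at Week 18". It also says: "The date and time of the drug administration and fasting conditions will be collected by the study site on the visit days".

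**Observation after that dose.** Protocol 1.3, Table 1, footnote e, schedules ECGs pre-dose and at 1 and 3 "hours post-dose on Day 1, Week 4, Week 16 and Week 20". Protocol 8.4.5 says of ECGs: "Any clinically significant findings will be reported as an AE".

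**Two neighbouring conventions.** SAP 5.2, in defining baseline relative to the first Part A dose, counts same-day assessments without a time as baseline, "except for adverse events (AEs) and medications starting on the first study treatment dose date which will be considered post-baseline". SAP 10 defines Part A concomitant medications as "any medications taken after the first dose of treatment and on or before or at week 16 visit", so it places the Week 16 visit in Part A.

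**The concern.** For a placebo subject the Week 16 visit day contains two exposures: placebo up to the on-site dose, and ASN002 80 mg from that dose on. A rule that uses only the calendar date gives the whole day to Placebo, including events that follow the active dose.

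The Part A Placebo column is the only concurrent control for AEs, and the counts of treatment-emergent and drug-related AEs are named secondary safety endpoints. An event that follows ASN002 but is counted under Placebo slightly narrows the apparent difference between drug and placebo. The randomised 40 mg and 80 mg groups do not have this problem, because their Week 16 dose is one more dose of the same treatment.

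**Working it through.** **Step 1: the boundary day.** Study day = 7 × week + 1. For Week 16 this is 7 × 16 + 1 = 113, which matches the D113 in Protocol Table 1.

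**Step 2: classify onsets in a placebo subject whose Week 16 visit falls on D113.**

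| Onset | Treatment last taken | Part under SAP 14.1 | Column |
|---|---|---|---|
| D112 | placebo | A | Placebo |
| D113, before the dose | placebo | A | Placebo |
| D113, after the dose | ASN002 80 mg | A | Placebo |
| D114 | ASN002 80 mg | B | Placebo/ASN002 80mg |

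Only the third row is misattributed.

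**Step 3: what the carry-over rule recovers.** If the third-row event lasts into Part B, it is counted under Placebo in Part A and again under Placebo/ASN002 80mg in Part B, with a note. If it resolves before Part B, the only AE summary it enters is the Part A Placebo one. Short-lived events are therefore the ones fully misplaced. Protocol 2.1.2 gives an example of that kind from Phase 1b, a transient headache seen mostly on Day 1. The protocol thinks fasting the likely cause, so it need not be a drug effect.

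**Step 4: the Day 1 convention.** SAP 5.2 gives the first Part A dosing day to the period after dosing. Applied by analogy to the first ASN002 dose at Week 16, it would put an untimed D113 onset in Part B. SAP 14.1 puts it in Part A. The two approaches agree on D112 and D114.

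**Step 5: size.**
- Subjects who could be affected: the plan allows up to 35 per group and assumes 25–30% dropout. If the placebo group loses that share before Week 16, 35 × 0.75 = 26.25 and 35 × 0.70 = 24.5, so roughly 24 to 26 subjects cross over.
- Effect per affected subject on a Part A Placebo percentage: 100 × 1/N. With N = 35 this is 2.86, or 2.9 points. With N = 25, the plan's figure before the dropout allowance, it is 4.0 points. Because 35 is the most the plan enrols per group, 2.9 is not an upper limit.
- A subject counts once per preferred term and once per system organ class. The percentage in a row therefore rises only if that subject had no earlier Part A event in the same row.
- The number affected would need a first-dose-day AE rate. The documents give none, so no total is computed.

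**The case against.** The case for leaving the rule alone has four parts.

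1. **It is not out of line with the rest of the SAP.** A reader might infer that SAP 14.1 contradicts SAP 5.2. It does not. SAP 5.2 concerns the first dose in Part A, and a Week 16 event is post-baseline under it either way. The closest parallel is the SAP 10 split of medications, which also puts the Week 16 visit in Part A, as does the visit schedule. This stands: the difference is one of convention at an analogous dosing day.

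2. **Most Week 16 findings do belong to Part A.** Protocol 1.3 has assessments precede dosing unless otherwise specified. Laboratory tests, vital signs and the pre-dose ECG at Week 16 therefore describe the placebo period. Protocol 8.7.5 lists an onset date but no onset time among the AE items, so a date rule is understandable. This stands, and any replacement must keep those findings in Part A.

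3. **The events remain visible.** Continuing AEs are shown in both parts, all AEs are listed, and SAP 14.4 gives ECG shift tables by timepoint. This stands, though a listing does not correct a summary count.

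4. **The consequences are small.** Protocol 9.3.3 rules out inference on safety variables, and Part B is described as supportive only. This also stands.

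A reader might also see undisclosed double counting in the carry-over rule. The text does not support that: the repeat is announced and flagged, and the column label Placebo/ASN002 80mg shows the crossover. What remains is a display matter. Treatment-emergent status is tied to the first Part A dose, so an unchanged AE that began on placebo still counts as treatment-emergent in Part B. Whether it would also enter the Combined ASN002 80mg column is not settled, because SAP 14 presents AEs by initial treatment and Appendix 1 offers that column only where applicable.

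None of this removes the third row of the table above.

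**Conclusion.** The point holds as a minor one. By its stated rule, SAP 14.1 attributes to Placebo an AE that begins after the first ASN002 dose on the Week 16 visit day. The event appears under Placebo alone if it resolves before Part B, and in both parts if it continues. Each affected subject is 1/N of the Placebo column, 2.9 points at N = 35. How many there would be cannot be said from the documents.

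This rests on reading Week 16 in SAP 14.1 as the visit day, as SAP 10 does. SAP 14.1 does not define the term and SAP 5.4 sets no windows. If nominal D113 were meant, a visit two days early (D111, within the ±2-day window) would put up to two further ASN002 days in Part A. That possibility is a reason to define the boundary, but the wider reading is not assumed here.

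A reader might infer that the safety comparison is materially biased. The documents do not support that: they give no AE rate, and the exposure is one calendar day per crossover subject. The effect is confined to descriptive safety tables. Efficacy, alpha, power and the attribution of AEs to dose in the randomised 40 mg and 80 mg groups are unaffected.

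**What to change.** - **Boundary.** In SAP 14.1, replace the reference to Week 16 with the date of each subject's first Part B dose, in all three groups. For subjects who never take a Part B dose, all AEs stay in Part A.
- **Same-day onsets.** Assign AEs starting on that date to Part B, unless they come from a pre-dose Week 16 assessment (for example laboratory tests, vital signs or the pre-dose ECG) or are otherwise documented as pre-dose. Those stay in Part A. Settle these cases before the Part A lock, while the sponsor and CRO are still blinded.
- **Part B display.** Count treatment-emergent AEs that are new or worsened since the first Part B dose separately from the unchanged carry-over AEs, which the SAP already flags. State whether the Combined ASN002 80mg column is used for AEs.
- **SAP 10.** Say whether the medication split follows the new boundary or keeps its own.

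**Cost.** A few lines of SAP text and a derivation from two dates already collected: AE onset (Protocol 8.7.5) and on-site dosing (Protocol 6.1). The pre-dose exception works only where the source or time of the finding is documented, so some case review may be needed. The downside is that some undocumented pre-dose onsets on that day will be classed as Part B. Because one rule applies to every group, the Part A observation period stays comparable across groups.

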1 PROTOCOL SUMMARY

1.1 Synopsis

Name of Sponsor/Company: Asana BioSciences, LLC	Name of Investigational Product: ASN002	Name of Active Ingredient: ASN002
Title of Study: A Randomized, Double-Blind, Placebo-Controlled, Phase 2 Study to Evaluate the Efficacy, Safety, Tolerability, and Pharmacokinetics of ASN002 in Subjects with Moderate to Severe Chronic Hand Eczema Refractory to Corticosteroid Therapy.		
Phase of Development: Phase 2		
Study Centers: Approximately 20-25 study centers located in the United States and Canada will participate in this study.		
Number of Subjects (planned): Approximately 105 subjects will be included in this study.		
Duration of Study: The maximum study duration per subject is up to 40 weeks (including up to 30 days for the screening period, followed by a 32-week treatment period, and up to 4 weeks for the follow-up period). The end of the study is defined as completion of the last visit or procedure shown in the schedule of event for the last enrolled subject in the trial globally for all sites.		
Investigational Product, Dosage, and Mode of Administration: ASN002 40 mg, 80 mg or placebo will be orally administered once daily during the treatment period. ASN002 will be available in 20-mg strength tablets. Subjects will be randomized in a 1:1:1 ratio to one of the following treatment regimens: 
– Part A: ASN002 40 mg (16-week treatment); Part B: ASN002 40 mg (16-week treatment)– Part A: ASN002 80 mg (16-week treatment); Part B: ASN002 80 mg (16-week treatment)– Part A: Placebo (16-week treatment); Part B: ASN002 80 mg (16-week treatment) Subjects who were assigned to regimen starting with a placebo in Part A (first 16 weeks) of the study will receive the highest dose of ASN002 (80 mg) for the rest of the treatment period (up to 32 weeks of treatment). Subjects who were assigned to ASN002 in the first part of the study will continue on the assigned treatment dose during the second part of the study up 32 weeks of treatment. The blind will be maintained until the primary efficacy analyses are locked for Part A and all safety data for Part A has been cleaned and monitored. The CRO team and the sponsor will be unblinded after the database lock of Part A and safety data review, but the sites, investigators and subjects will remain blinded throughout the study. Randomization will be stratified for the biopsy collection and for the PGA score of '3' (moderate) or '4' (severe).		

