DLQI		X	X	X	X	X	X		X	X	X	X	X

Study Visits	Screening	Treatment Period											Follow-up / ET
		Part A						Part B					
Day (D); Week (W)		D1	W2 (D15)	W4 (D29)	W8 (D57)	W12 (D85)	W16 (D113)	W18 (D127)	W20 (D141)	W24 (D169)	W28 (D197)	W32 (D225) EOT ^a	W36 (D253) EOS
Window (days)	-30 to -1		±1	±1	±2	±2	±2	±2	±2	±2	±2	±2	±2
WPAI-SHP		X	X	X	X	X	X		X	X	X	X	X
Pain Visual Analog Scale		X	X	X	X	X	X		X	X	X	X	X
Skin microbiome analysis [worst hand (palmar aspect, when possible) involved with eczema (and plantar aspect (when possible) of foot, if foot involvement)] ⁱ		X		X			X						X ^j
Tape strips collection [from hand (and foot if applicable)] ^k		X		X			X						X ^j
Skin biopsies collection ^l		X		X ^m			X						X ^j
Blood sampling for PD analyses ⁿ		X		X ^m			X						X ^j
Blood sampling for PK evaluation		X ^o	X ^p	X ^o	X ^p	X ^p	X ^p		X ^p	X ^p	X ^p	X ^p	X ^{f,p}
Randomization		X											
Study product administration at study center		X	X	X	X	X	X		X	X	X	X	
Study product administration daily ^q		X-----											
Emollient use on hands and feet (if foot eczema) ^r		X-----											X
Dispensing of study product		X		X	X	X	X ^s		X	X	X		
Study product collection/accountability/compliance ^t			X ^u	X	X	X	X		X	X	X	X	X ^f
Photograph of both aspects (palmar and dorsal) of both hands ^v		X			X		X			X		X	X
Concomitant medication	X	X	X	X	X	X	X	X	X	X	X	X	X
Adverse events evaluation	X	X	X	X	X	X	X	X	X	X	X	X	X

BSA=Body Surface Area; DLQI=Dermatology Life Quality Index; ECG=electrocardiogram; EOS=end of study; EOT=end of treatment; ET=early termination; HBV=hepatitis B virus; HCV=hepatitis C virus; HECSI=hand eczema severity index; HIV=human immunodeficiency virus; mTLSS=modified Total Lesion

Study Visits	Screening	Treatment Period											Follow-up / ET
		Part A						Part B					
Day (D); Week (W)		D1	W2 (D15)	W4 (D29)	W8 (D57)	W12 (D85)	W16 (D113)	W18 (D127)	W20 (D141)	W24 (D169)	W28 (D197)	W32 (D225) EOT ^a	W36 (D253) EOS
Window (days)	-30 to -1		±1	±1	±2	±2	±2	±2	±2	±2	±2	±2	±2

Symptom Score; PaGA=Patient Global Assessment; PD=pharmacodynamic; PGA=Physician's Global Assessment; PK=pharmacokinetics; VAS=visual analog scale; WPAI-SHP=Work Productivity and Activity Impairment – Specific Health Problem.

^a The end of treatment (EOT) visit will occur on the first day of Week 32 (D 225) (+/- 2 days).

^b Females of childbearing potential only. Serum pregnancy test at screening and urine pregnancy test at other visits.

^c Brief physical examinations.

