4 STUDY DESIGN

4.1 Overall Design

This study will be performed at approximately 20-25 study centers located in the United States and Canada.

Approximately 105 subjects with moderate to severe CHE (as defined by a hand PGA 3 or 4 at Day 1) will be included in this randomized, double-blind, placebo-controlled, multicenter, Phase 2 study. Subjects will be men or women, 18 years of age or older, at the time of consent. Subjects with moderate CHE will be limited to 30% of total enrollment.

Each subject should read and sign an informed consent form prior to any screening procedures being performed. Subjects who fulfill all of the inclusion criteria and none of the exclusion criteria will be accepted into the study. After a screening period of no more than 30 days (from Day -30 to Day -1), eligible subjects will be randomized (1:1:1) on Day 1 to receive ASN002 at 40 mg or 80 mg, or placebo once daily for 16 weeks (Part A). Then, in Part B, subjects who were assigned to placebo in the first part of the study will receive the highest dose of ASN002 (i.e. 80 mg) for the rest of the treatment period (up to Week 32). The subjects who were assigned ASN002 in the first part of the study will continue on the same assigned treatment dose during the second part of the study (Week 16 to Week 32). The total treatment period of 32 weeks will be followed by a 4-week follow-up period. For scheduled study visits, subjects will come to the study centers on 13 occasions: screening; Day 1; Weeks 2, 4, 8, 12, 16, 18, 20, 24, 28 and 32; and Week 36 (follow-up visit)/early termination (ET).

Efficacy will be assessed using mTLSS, PGA, HECSI, pain VAS and Extent of Disease. In addition, a 6-grade PaGA scale will be used. Quality of life will be evaluated using DLQI. Impact on work productivity and activity will be studied using the WPAI-SHP questionnaire.

Safety will be assessed by collecting AEs, recording vital signs, performing physical examination and 12-lead ECG, and evaluating clinical laboratory tests.

Pre- and post-dose PK blood samples will be collected from all subjects on a sparse sampling schedule on Day 1 and Weeks 2, 4, 8, 12, 16, 20, 24, 28, and 32 (or ET visit, if applicable).

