8.7 Adverse Events and Serious Adverse Events

8.7.1 Definition of Adverse Event

An AE is any untoward medical occurrence in a subject administered a pharmaceutical product and that does not necessarily have a causal relationship with this treatment. An AE can therefore be any unfavorable and unintended sign (including an abnormal laboratory finding), symptom, or disease temporally associated with the use of a study product, whether or not considered related to the study product. AEs and SAEs will be collected from the time of informed consent signature until the final visit / contact.

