14 SAFETY ANALYSIS

All safety analyses will be conducted using the safety population and will be presented combined except adverse events, which will be presented separately for Part A and Part B. For both parts subjects will be presented by their initial treatment as assigned in Part A.

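### Part B TEAE tables take in the 4-week off-drug follow-up, so crude TEAE counts and percentages are not comparable between Part A and Part B

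*SAP*

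**What the plan says.** SAP 14 reports safety combined over the two parts, except for "adverse events, which will be presented separately for Part A and Part B". SAP 14.1 gives the dividing rule: "if the AE onset date was on or before week 16 the AE will be considered as a Part A AE", and "If the AE had an onset after week 16 the AE will be considered as a Part B AE". An event that starts in Part A and continues is reported again in Part B, with a note.

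The new-onset limb of the SAP's TEAE definition covers "any condition that was not present prior to treatment with the study product but appeared following first dose in Part A". Only the other two limbs (worsening, and resolution followed by reappearance) are tied to being on treatment. Protocol 8.7.2 is also open-ended for new conditions.

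Protocol 4.1 states: "The total treatment period of 32 weeks will be followed by a 4-week follow-up period". Protocol 8.7.1 states: "AEs and SAEs will be collected from the time of informed consent signature until the final visit / contact". The Schedule of Events evaluates adverse events at the Week 36 visit.

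In SAP Appendix 1 every Part B column is an ASN002 column, and no follow-up period is defined. The default percentage denominator is the number of subjects in the population per treatment group. SAP 14.1 plans numbers of events and numbers and percentages of subjects. It plans no exposure-adjusted rate.

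**The concern.** The secondary safety endpoints are the number of TEAEs and the number of drug-related TEAEs, and the AE tables are produced by part. Placebo exists only in Part A. A reader interested in longer exposure, or in what happens when placebo subjects move to 80 mg, will set the two tables side by side. Those tables cover windows of different length. One is entirely on assigned treatment for a completer, while the other mixes on-drug and off-drug time under an ASN002 label. Without a split, a reader cannot tell whether a difference reflects the drug, the longer window, the drug-free weeks or the change in who is still in the study.

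**Working it through.** **Inputs.** Visit days come from the Schedule of Events (Protocol 1.3): Week 16 is Day 113, Week 32 (end of treatment, with a dose at the site) is Day 225, and Week 36 (end of study) is Day 253. The window rules come from SAP 14.1. Mean half-life is 7.3 to 13.7 hours (Protocol 2.1.2). Sample size of up to 35 per group and dropout of 25-30% come from SAP 5.1. The target of 75 subjects completing Week 16 comes from the protocol version history, entry 6.0.

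**Timeline.** Visit day = 7 × week + 1 gives 113, 225 and 253, as scheduled. The synopsis says "The maximum study duration per subject is up to 40 weeks". Its components give 30/7 + 32 + 4 = 40.3 weeks, which agrees.

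**Scheduled TEAE window for a completer.**

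- Part A: Day 1 to Day 113 = 113 days (16.1 weeks).
- Part B: Day 114 to Day 253 = 253 − 113 = 140 days (20.0 weeks). The ±2-day tolerances at Weeks 16 and 36 give 251 − 115 = 136 to 255 − 111 = 144 days.
- Part B on treatment: 225 − 113 = 112 days.
- Part B after end of treatment: 253 − 225 = 28 days, and 28/140 = 20%.
- Ratio: 140/113 = 1.24.

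**How much of the 28 days is drug-free.** Five half-lives take 5 × 7.3/24 = 1.5 days to 5 × 13.7/24 = 2.9 days. That leaves about 25 to 26 days.

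**Effect on subject percentages.** The documents give no incidence, so p below is an assumed 16-week risk with a constant hazard. For completers only, the 20-week risk is 1 − (1 − p)^(20/16).

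To allow for dropout, assume that 25 of 35 subjects enter Part B, the other 10 leave uniformly over Part A and contribute no events afterwards, and nobody leaves during Part B. The average risk for a dropout is 1 − p/(−ln(1 − p)). Then:

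- Part A % = [25p + 10 × (1 − p/(−ln(1 − p)))]/35
- Part B % on the full group = 25 × [1 − (1 − p)^1.25]/35

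| p | Completers, 20 weeks | Part A, N = 35 | Part B, N = 35 | Part B, N = 25 |
|---|---|---|---|---|
| 20% | 24.3% | 17.2% | 17.4% | 24.3% |
| 40% | 47.2% | 34.8% | 33.7% | 47.2% |
| 60% | 68.2% | 52.7% | 48.7% | 68.2% |

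With no drug effect at all, Part B can look the same as, lower than or higher than Part A, depending on the denominator.

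**Person-time under the same dropout pattern.** At 25% dropout, Part A has 26.25 × 16 + 8.75 × 8 = 490 patient-weeks. Part B has 26.25 × 20 = 525, of which 26.25 × 16 = 420 are on drug. At 30%, Part A has 24.5 × 16 + 10.5 × 8 = 476. Part B has 24.5 × 20 = 490, of which 24.5 × 16 = 392 are on drug. Part B therefore has more observation time but less on-drug time than Part A.

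**After a cut at last dose.** A completer's windows become 112 days (Part B) against 113 (Part A). If a margin of five half-lives were added, Part B would be about 114 to 115 days.

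**The case against.** The case for leaving the plan alone has several parts.

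- **No formal comparison is affected.** Protocol 9.3.3 rules out inferential statistics on safety, Part B is supportive only, the placebo comparison lies within Part A, and all arms in Part B share the same scheduled window. This stands, and it limits the consequence to a descriptive reading across tables.
- **Post-treatment events can be traced.** Protocol 9.3.3 shows AE onset in days relative to dosing, all AEs are listed, and days treated are summarised. This is true at subject level, but it does not repair the summary tables.
- **Keeping follow-up events is prudent.** The events of clinical interest include thrombosis, serious infection and malignancy. Clearance of drug from plasma does not show that such an event is unrelated. This stands: follow-up events should stay in the report.
- **A cut in Part B alone would create a new asymmetry.** Subjects who stop early in Part A can also contribute events after their last dose, up to the early termination visit. This also stands, and it shapes the fix.

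A reader might also infer four stronger things that the documents do not support:

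- **That the imbalance affects all AE rows.** It affects TEAEs. Events are collected from consent, so screening events fall in Part A, where the all-AE window is up to 30 + 113 = 143 days against 140 in Part B.
- **That the plan attributes off-drug events causally to ASN002.** Causality is a separate investigator rating (Protocol 8.7.4.1). The column label is tabulation only, although SAP 14.1 counts an unknown relationship as treatment-related.
- **That hand eczema rebound after stopping treatment would appear as an adverse event.** Protocol 8.7.5 says worsening of CHE is not recorded as one.
- **That Part B percentages must be inflated.** The dropout calculation shows that they need not be.

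**Conclusion.** The point holds for TEAEs. Neither document sets an end date for new-onset TEAEs or a separate follow-up period, so Part B TEAE tables under ASN002 columns mix 112 scheduled on-drug days with 28 days after end of treatment. A completer's Part B window is about 1.24 times the Part A window. Crude counts and percentages from the two parts should not be read against each other.

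The direction of the net distortion is not known. The longer window raises Part B figures for completers. Dropout combined with the default population denominator lowers them. Event rates may also differ once drug is stopped. The window lengths follow from the schedule. The percentages in the table rest on an assumed constant hazard and, apart from the completer column, on an assumed dropout pattern, so they illustrate the mechanism and predict nothing.

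No efficacy result, planned test or within-Part-B comparison of scheduled windows changes. The change is worth making because it is cheap and makes the TEAE-count endpoints interpretable by part.

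**What to change.** In SAP 14.1, before database lock:

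1. Keep collecting and reporting every follow-up AE.
2. Flag each TEAE by onset as on-treatment or post-last-dose. Use one pre-stated cut-off relative to last dose, applied identically in Part A (including early terminators) and Part B.
3. Tabulate post-treatment onsets separately, and use the on-treatment set wherever Part A and Part B tables are to be read together.
4. State that the Part B denominator is subjects dosed in Part B.
5. Add exposure-adjusted TEAE rates (events per 100 patient-weeks) for each part, counting person-time over the same interval as the events. Base the Part B rate on new onsets, so that continuing Part A events are not counted twice.

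The cost is SAP wording, one period flag and one extra set of tables. SAP 11 already uses first and last dose dates for compliance, so no new data are needed and trial conduct does not change.
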